CLINICAL TRIAL PROTOCOL

Protocol Title: The effect of dolutegravir on whole-body insulin sensitivity, lipid and endocrine profile in healthy volunteers

Protocol Number: CRF003

Version Version 4.0 20 Jan 2023

[figure not shown]
EudraCT No: 2020-004395-17

IRAS Number: 274870

Clinical Trial.gov: NCT04771754

Chief Investigator: [name]
St. Stephen's Centre
Chelsea and Westminster Hospital NHS Foundation Trust
[name]
[name]

Sponsor: Chelsea and Westminster Hospital NHS Foundation Trust
[name]
[name]

Protocol Approval: 
[name]

20 Jan 2023
dd mmm yyyy

GCP Compliance Statement:

This trial will be conducted in compliance with the protocol, the principles that have their origin in the Declaration of Helsinki and all applicable regulatory requirements

Synopsis

Name of Investigational Product:	Dolutegravir
Name of Active Ingredients:	Dolutegravir
Study Title:	The effect of dolutegravir on whole-body insulin sensitivity, lipid and endocrine profile in healthy volunteers
Phase of Study:	Phase I
Objectives:	
The objectives of this study are:
 
Primary
 
To quantify the difference in change in insulin sensitivity (determined by peripheral glucose uptake using a euglycaemic clamp) with the administration of dolutegravir (DTG) compared to no DTG for 28 days in HIV seronegative healthy volunteers.
 
Secondary
 
To investigate the effect of the dolutegravir on:
 
1. Adipocytokines by assessing adiponectin and leptin levels2. Ghrelin3. Pituitary hormones4. Lipid profile including lipid fractions5. Changes in indirect calorimetry6. Changes in food intake by food diaries7. Change in sleep parameters by sleep questionnaires8. Safety and tolerability of dolutegravir

Study Design	Randomised, crossover
Indication:	HIV negative volunteers
Methodology:	Insulin sensitivity determined by glucose disposal during steady state of euglycaemic clamp.
Planned Sample Size:	16
Summary of Eligibility Criteria:	
 • HIV negative subjects • Clinically well • BMI between 18 and 30kg/m² • Free from diabetes mellitus and metabolic syndrome • Not receiving any metabolically active medication or drugs likely to interact with antiretroviral therapy • Able and willing to provide informed consent
Number of Study Centres	One
Duration of Treatment:	28 days per sequence with washout between sequences
Dose and Route of Administration:	Orally administered dolutegravir 50 mg once daily
Criteria for Evaluation:	Subjects will undergo three euglycaemic clamp procedures in order to determine the extent of glucose disposal. The first clamp will be performed prior to the commencement of the first study drug administration/no treatment, the second one following four weeks of study drug/no treatment, the third after the crossover phase to study drug/no treatment.
Primary Endpoint:	Change from baseline in total body glucose disposal by euglycaemic clamp method following 28 days treatment

Secondary Endpoints:

- Change from baseline in serum levels of fasting cholesterol fractions and triglycerides
- Changes from baseline in serum adipocytokines, ghrelin and pituitary hormones
- Changes from baseline in indirect calorimetry
- Caloric intake by food diaries
- Quality of sleep by sleep questionnaires
- Safety data including the number and severity of adverse events, as assessed by the medical dictionary for regulatory activities (MedDRA), from baseline to day 100

General Study Information

Name of sponsor:	Chelsea and Westminster Hospital NHS Foundation Trust [name]
Chief investigator:	[name] Chelsea and Westminster Hospital [name] [contact]
Co-Investigator	[name] Chelsea and Westminster Hospital [name] [contact]
Laboratory facilities: Biochemistry & Haematology	Imperial College NHS Foundation Trust Pathology Laboratory Chelsea and Westminster Hospital [name]
Virology & Hepatitis	Imperial College NHS Foundation Trust Dept. of Infection & Immunity [name] Charing Cross Hospital [name]

Medical expertise:	[name] & [name] Chelsea and Westminster Hospital [name] [contact]
Data management and Statistics:	Research and Development Office Chelsea and Westminster Hospital NHS Foundation Trust [name]
Monitor:	Research and Development Office Chelsea and Westminster Hospital NHS Foundation Trust [name] [contact] Email: [contact]

List of abbreviations and definitions of terms

ACTG	AIDS Clinical Trial Group
AE	Adverse event
AIDS	Acquired Immune Deficiency Syndrome
ALT	Alanine aminotransferase
AST	Aspartate aminotransferase
BMI	Body Mass Index
CM	Concomitant Medication
CRF	Case Report Form
DAIDS	Division of AIDS

1.1 Introduction & background

Metabolic changes and weight increase commonly occur early in ART. Weight gain observed in many patients shortly after ART initiation is thought to be due in part to a reduction in basal metabolic rate following suppression of plasma viremia, improved appetite, lower inflammatory cytokine effects and a reduction in the rate of protein turnover [1, 2].

Multiple studies in healthy volunteers have demonstrated acute onset of reversible insulin resistance, as assessed by euglycaemic hyperinsulinaemic clamp, inhibition of glucose transporters, in particular GLUT4, with protease inhibitors (PIs) and difference in effects on insulin resistance and other metabolic parameters is seen as a key differentiator of agents within the PI class. Other antiretroviral drug classes have also been extensively tested. Clinical cohort data and data from clinical trials have reported an association between some nucleoside reverse transcriptase inhibitors (NRTIs) (stavudine, zidovudine, didanosine) and insulin resistance or diabetes mellitus. As mitochondrial dysfunction has been proposed as playing a role in the pathogenesis of diabetes mellitus, the association with drugs which may impact mitochondrial DNA and diabetes is not surprising. Tenofovir DF use does not cause insulin resistance when investigated with euglycemic clamp methodology [3].

A recent case report of acute onset diabetes mellitus after a switch to an Integrase Strand Transfer Inhibitor (INSTI)-containing regimen (raltegravir/abacavir/lamivudine) postulated effects on bioavailable magnesium could alter insulin signalling characteristics [4].

The association between insulin resistance and body shape changes and weight gain during therapy has not been established. Insulin resistance triggered by some ARV drugs is apparently reversible, following switching to an agent not associated with insulin resistance. However, reduction in central adiposity has only been observed in highly selected subject, [5] weight gain in the setting of HIV may not be exclusively related to glucose and/ or fat handling, but may also relate to alterations in endocrine function, therefore we proposed study to investigate changes in insulin resistance, lipid metabolism and complete endocrine profile in subject exposed to dolutegravir to investigate the role all these different factors may potentially have in weight gain recently reported in clinical cohorts.

1.2 Rationale

In a retrospective analysis in the NA-ACCORD, 22% of those with normal BMI at the start of anti-retroviral therapy (ART) became overweight after 3 years of ART, and 18% of those overweight at baseline becoming obese [1]. And a recent retrospective analysis by Menard et al [6] on patients stopping dolutegravir (DTG) due to adverse effects in the clinical setting, found that 7% had done so due to weight gain. Norwood and colleagues [7] has reported significantly increased weight gain in those switching to an INSTI-based regimen from an efavirenz-based (Atripla) based regimen. This weight gain was greatest among patients switching to DTG/ABC/3TC [7]. The etiology of weight gain in patients with undetectable plasma HIV RNA who change to another regimen and remain suppressed is unclear. An abrupt reduction in insulin sensitivity could

promote storage of excess circulating glucose and lipids in adipose tissue, but this is was speculative until now, therefor we propose the study of insulin sensitivity to address the underlining reasons for weight change in patients receiving dolutegravir based therapy.

Other studies have used a range of ART for 28 days in healthy volunteers looking at similar metabolic, coagulation and inflammatory markers and pharmacokinetic [8-11]. Given DTG half-life we wished to establish steady state to adequately examine the effect of a drug on weight gain, lipids and neuroendocrine markers. 28 days of DTG is Centre for Disease Control (CDC) recommended post exposure prophylaxis (PEP), therefore this duration of dosing is widely used and recommended in HIV-negative individuals [12].

HYPOTHESIS: There is no difference in change in insulin resistance and multiple lipid parameters in healthy volunteers when treated with dolutegravir compared with baseline values.

2. Trial Objectives

2.1 Primary Objective

To quantify the difference in change in insulin sensitivity (determined by peripheral glucose uptake using a euglycaemic clamp) with the administration of dolutegravir (DTG) compared to no DTG for 28 days in HIV-seronegative healthy volunteers.

2.2 Secondary Objectives

To investigate the effect of the dolutegravir on:

1. Adipocytokines by assessing fasting adiponectin and leptin levels
2. Fasting Ghrelin
3. Pituitary hormones
4. Lipid profile including lipid fractions
5. Changes in indirect calorimetry
6. Changes in food intake by food diaries
7. Change in sleep parameters by sleep questionnaires
8. Safety and tolerability of dolutegravir

3. Trial Design

3.1 Endpoints

Primary Endpoint

- Change from baseline in total body glucose disposal by euglycaemic clamp method with 28 days dolutegravir treatment.

Secondary Endpoints

- Change from baseline in serum levels of fasting cholesterol and triglycerides
- Changes in adipocytokines, ghrelin and pituitary hormones
- Changes in indirect calorimetry
- Changes in food intake by food questionnaires
- Changes in sleep quality by sleep questionnaires
- Safety data including the number and severity of adverse events, as assessed by the medical dictionary for regulatory activities (MedDRA), from baseline to day 100

3.2 Study design

This is a 72-day (excluding screening period and follow up phone call) randomized study with two arms. The study will utilize a crossover design as described below.

Subjects will be randomised to start on dolutegravir 50 mg once daily OR no treatment for the first 28 day dosing phase of the study, then will cross over to the alternative for the second dosing phase, following a 2 week washout period (equivalent to 5+ dolutegravir elimination half-lives). Subjects will be contacted approximately seven days after the final euglycaemic clamp visit for a telephone follow up.

- **Day -28 to 0:** Screening
- **Day 1 (am):** Euglycaemic clamp 1
- **Day 1 (pm) to 28:** Dolutegravir (n=8)/Control (n=8)
- **Day 28 (am):** Euglycaemic clamp 2
- **Day 29 to 43:** Wash out (14 days)
- **Day 44 to 72:** Control (n=8)/Dolutegravir (n=8)
- **Day 72 (am):** Euglycaemic clamp 3
- **Day 100** Post study telephone contact

3.3 Randomisation

After screening, eligible subjects satisfying the inclusion and exclusion criteria will be randomised 1:1 to one of two arms:

Group 1:

- Dolutegravir 50 mg once daily for the first 28 days of the study.
- No treatment for the last 44 days of the study.

Group 2:

- No treatment for the first 43 days of the study.
- Dolutegravir 50 mg once daily for the last 28 days of the study (day 44-72).

3.4 Benefit: Risk Assessment

- Key identified and potential risks of DTG and the clamp procedure are summarized in Appendix 4. More detailed information about the known and expected risks and reasonably expected adverse events (AEs) of DTG may be found in the SmPC for Tivicay. (Appendix 4)

4. Subject Population

4.1 Number of subjects and subject selection

Subjects will be HIV-1 negative volunteers aged between 18 to 60 years inclusive. The total number of subjects recruited will be 16 (8 per group)

4.1.1 Inclusion Criteria

- Willing and able to provide informed consent
- Cis-Male and Cis-Female healthy subjects without underlying conditions
- Subjects must have documented negative HIV serology by ELISA and P24 antigen and not receiving anti-HIV pre-exposure prophylaxis (PreP)
- Subjects must be clinically well volunteers aged between 18 to 60 years with BMI <30 kg/m² but >18 kg/m²
- Healthy, as determined by the investigator or medically qualified designee based on a medical evaluation, including medical history, physical examination, laboratory tests, and cardiac evaluation (including ECG)
- Non-fasting blood glucose, total cholesterol and triglycerides within normal limits
- Subjects should have complete blood count (FBC) with normal differential and platelet count (detail below of specified normal range, table 1)

Table 1 – Compete FBC with normal differential & platelets count ranges

Test	Male Normal Range	Female Normal Range
Haemoglobin (g/L)	130-168	114-150
White blood cell count ($\times 10^9$ /L)	4.2-10.6	4.2-11.2
Neutrophil count ($\times 10^9$ /L)		2.0 - 7.1
Lymphocyte count ($\times 10^9$ /L)		1.1 - 3.6
Monocyte count ($\times 10^9$ /L)		0.2 - 0.9
Eosinophil count ($\times 10^9$ /L)		0.0 - 0.5
Basophil count ($\times 10^9$ /L)		0.0 - 0.2

- A female, may be eligible to enter and participate in the study if she:
 - is of non-child-bearing potential defined as either post-menopausal (12 months of spontaneous amenorrhea and ≥ 45 years of age) or physically incapable of becoming pregnant with documented tubal ligation, hysterectomy or bilateral oophorectomy or,
 - is of child-bearing potential with a negative pregnancy test at both Screening and Day 1 and agrees to use one of the following methods of contraception to avoid pregnancy:
 - Complete abstinence from penile-vaginal intercourse. Abstinence is acceptable only as true abstinence when this is in line with the preferred and usual lifestyle of the participant;
 - Any intrauterine device with published data showing that the expected failure rate is $<1\%$ per year (not all intrauterine devices meet this criterion, see Appendix 6] for an example listing of approved intrauterine devices);
 - Male partner sterilization confirmed prior to the female subject's entry into the study, and this male is the sole partner for that subject;
 - Approved hormonal contraception (see Appendix 6] for a listing of examples of approved hormonal contraception)*;
 - Any other method with published data showing that the expected failure rate is $<1\%$ per year
- Men who have partners who are women of childbearing potential (WOCBP – definition in Appendix 6) must be using an adequate method of contraception to avoid pregnancy in their partner throughout the study and for a period of at least 4 weeks after the study;
 - Complete abstinence from penile-vaginal intercourse. Abstinence is acceptable only as true abstinence when this is in line with the preferred and usual lifestyle of the patient;
 - Double barrier method (male condom/spermicide, male condom/diaphragm, diaphragm/spermicide);

- Any intrauterine device (IUD) with published data showing that the expected failure rate is <1% per year (not all IUDs meet this criterion, see Appendix 4 for an example listing of approved IUDs) plus male condom;
- Sterilisation confirmed prior to the subject's entry into the study
- Approved hormonal contraception used by female partner (see protocol appendix 4 for a listing of examples of approved hormonal contraception) plus male condom;
- Any other method with published data showing that the expected failure rate is <1% per year and not containing hormones plus male condom.
- Any contraception method must be used consistently, in accordance with the approved product label and for at least four weeks after discontinuation of IMP (Appendix 6).

Any contraception method must be used consistently, in accordance with the approved product label and for at least 28 days prior to the first dose of study medication and 4 weeks after discontinuing the study medication.

4.1.2 Exclusion Criteria

- Subjects with a waist hip ratio > 0.97 or BMI > 30kg/m² and BMI < 18 kg/m² will be excluded
- Acute or chronic hepatitis B infection (determined by positive hepatitis B surface antigen result at the screening visit)
- Acute or chronic hepatitis C infection (determined by positive hepatitis C antibody result at the screening visit)
- Diabetes mellitus, other metabolic syndrome or disease process in the opinion of the investigator likely to cause marked disturbance in glucose and lipid homeostasis including hypertension. Subject with HbA1c >42 mmol/mol will be excluded.
- History or presence of allergy to the dolutegravir
- ALT or AST greater than or equal to 1.5 x Upper Limit of Normal (ULN) and total bilirubin greater than or equal to 1.5 x ULN excluded;
- Pregnancy and breastfeeding women
- Alcohol consumption >10 units/week
- Clinically relevant drug use (positive urine drug screen) or history of alcohol or drug use considered by the Investigator to be sufficient to hinder compliance with treatment, follow-up procedures or evaluation of adverse events. Smoking is permitted, but tobacco intake should remain consistent throughout the study.
- Unable to refrain from the use of prescription (e.g., dofetilide) or non-prescription drugs, including vitamins, herbal and dietary supplements (including St John's wort) within 7

days (or 14 days if the drug is a potential enzyme inducer) or 5 half-lives prior to the baseline visit and throughout the study until the follow-up period, unless in the opinion of the Investigator the medication will not interfere with the study procedures or compromise participant safety.

- This includes on-going therapy with any of the following
 - Metabolically active medications
 - Any lipid-lowering medication
 - Any testosterone treatments or supplements - Glucocorticoids including inhaled steroids except for 'as necessary' use
 - Beta-blockers
 - Thiazide diuretics and indapamide
 - Thyroid preparations
 - Psychotropic agents
 - Anabolic steroids
 - Megestrol acetate
 - Dofetilide (or pilsicainide)

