Appendix 1: Study flowchart

	Screen (-28)	Baseline	Day 28	Day 44	Day 72	Follow-up call (Day 100)
Informed consent	✓					
Physical Exam	✓					
Medical history	✓					
Demographics	✓					
Vital signs	✓	✓	✓	✓	✓	
Weight	✓	✓	✓	✓	✓	
Height, waist/hip measurement	✓	✓	✓	✓	✓	
Adverse Events		✓	✓	✓	✓	✓
Concomitant medication	✓	✓	✓	✓	✓	
Urinary analysis ¹ and Urine drug testing	✓	✓	✓	✓	✓	
Biochemistry ²	✓ ³	✓	✓	✓	✓	
Haematology ⁴	✓	✓	✓	✓	✓	
Pregnancy testing ⁵	✓	✓	✓	✓	✓	✓
Insulin		✓	✓		✓	
TSH, fT4		✓	✓	✓	✓	
HIV, HBV &HCV	✓					

CRP		✓	✓	✓	✓	
Adiponectin, leptin, ghrelin		✓	✓	✓	✓	
Pituitary hormone tests		✓	✓	✓	✓	
Testosterone		✓	✓	✓	✓	
Euglycaemic clamp		✓	✓		✓	
ECG	✓	✓	✓		✓	
Indirect calorimetry		✓ ⁶	✓ ⁷		✓ ⁸	
Dietary Questionnaire		✓	✓	✓	✓	
Sleep Questionnaires		✓	✓	✓	✓	
Self-administered dosing		✓ ⁷ (am)	✓ ⁷	✓ ⁸ (am)	✓ ⁸	
Drug Dispensing		✓ ⁷		✓ ⁸		
Drug returns			✓ ⁷		✓ ⁸	

1-urinary analysis (pH, specific gravity, leucocytes, nitrite, protein, glucose, ketones, urobilinogen, bilirubin, erythrocytes)

2-Biochemistry safety labs assessment for standard clinical chemistry (glucose, creatinine, sodium, potassium, calcium, aspartate aminotransferase, alanine aminotransferase, bilirubin), lipids (triglycerides, cholesterol, cholesterol HDL & LDL Sub-fractions) and Hb1Ac

3-screening visit is not fasting visit

4-haematology (haemoglobin, haematocrit, erythrocyte count, white blood count, differential white blood cell count, platelets)

5- Pregnancy testing and LMP date in female subjects

6- All participants

7-only Group 1

8-only Group 2

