Drug induced liver injury and other clinically significant liver chemistry elevations	
Non-clinical data suggested a possible, albeit low, risk for hepatobiliary toxicity with DTG. Drug-related hepatitis is considered an uncommon risk for antiretroviral therapy containing DTG regardless of dose or treatment population.
	
Subjects meeting any of the following criteria during the screening period are excluded from participating
 
 • Alanine aminotransferase (ALT) or Aspartate aminotransferase (AST) ≥ 1.5 times the upper limit of normal (ULN) or total bilirubin $\geq 1.5 \times$ULN 
Positive for HBV (hepatitis B virus surface antigen positive [+HBsAg]) or positive HCV (positive hepatitis C antibody test) within 3 months of the Day 1 study visit
 
Specific/detailed liver stopping criteria and toxicity management guidance are provided for suspected drug induced liver injury or other clinically significant liver chemistry elevations

Neural Tube Defects	
In the ongoing observational study conducted in Botswana, preliminary results show that in babies born to women who were taking DTG when
	
Pregnancy testing should be performed before initiation of DTG therapy in all women of child bearing potential (negative)

Potential Risk of Clinical Significance	Data/Rationale for Risk	Mitigation Strategy
Investigational Product: dolutegravir Refer to the most recently approved SmPC for this trial		
	
they became pregnant there was an increased risk of neural tube defects compared with the background rate.
 
Dolutegravir was tested in a complete package of reproductive toxicology studies, including embryofoetal development studies. No adverse development outcomes, including neural tube defects, were identified from reproductive toxicology studies. In reproductive toxicity studies in animals, DTG was shown to cross the placenta.
 
Data available from other sources including the Antiretroviral Pregnancy Registry (APR), other cohorts and clinical trials are insufficient to confirm or refute this potential risk.
	
pregnancy test at screening and randomization).
 
Women who are pregnant or who plan to become pregnant are excluded.
 
All women of reproductive potential should use effective contraception (Appendix 6).
 
The subject informed consent form provides information about this potential risk.

Risk Assessment: Clamp procedure

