Appendix 5: Liver Chemistry Stopping and Follow up Criteria

Dolutegravir must be discontinued if:

- AST or ALT \geq 3xULN.
- If AST or ALT \geq 3xULN AND bilirubin >2xULN (>35% direct bilirubin), i.e. Hy's case, report event as SAE.

Required Actions and Follow up Assessments following ANY Liver Stopping Event	
Actions	Follow Up Assessments

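### The liver exclusion in Section 4.1.2 joins its two limits with *and* where Appendix 4 uses *or*, so read literally it admits a volunteer with only one abnormality

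*Combined protocol and SAP*

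**What the plan says.** Section 4.1.2 handles liver chemistry at entry in a single bullet. It sets a floor for either transaminase and runs straight on to bilirubin: "1.5 x Upper Limit of Normal (ULN) and total bilirubin greater than or equal to 1.5 x ULN excluded".

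Appendix 4, in the row on drug-induced liver injury, describes the same exclusion as the mitigation for that risk. It opens with "Subjects meeting any of the following criteria during the screening period are excluded from participating" and then lists ALT or AST at or above 1.5 "times the upper limit of normal (ULN) or total bilirubin" at or above 1.5 x ULN. Section 3.4 relies on this appendix: "Key identified and potential risks of DTG and the clamp procedure are summarized in Appendix 4".

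Three other places bear on the point:

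- Section 4.1.1 has a general criterion, "Healthy, as determined by the investigator or medically qualified designee based on a medical evaluation". The evaluation includes laboratory tests, but no ALT, AST or bilirubin limit is given.
- Appendix 5 sets the on-treatment rule. Under "Dolutegravir must be discontinued if" it lists AST or ALT at or above 3 x ULN.
- Appendix 1 and Section 6 schedule liver chemistry at screening and on Days 1, 28, 44 and 72.

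**The concern.** The protocol holds two versions of one eligibility rule, and the looser version sits in the list that governs entry. Section 3.3 randomises those who satisfy the inclusion and exclusion criteria, and Section 6 admits those who meet them at baseline. Those criteria are in Section 4.1. Appendix 4 is a risk table, and staff need not consult it at screening.

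If Section 4.1.2 is followed literally, the mitigation that the benefit-risk assessment describes is not delivered. A healthy volunteer with an isolated transaminase rise could be given a drug for which Appendix 4 acknowledges a low hepatobiliary risk. Two screeners could also decide differently on the same result. A monitor would then find the same enrolment consistent with Section 4.1.2 and contrary to Appendix 4.

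**Working it through.** No power or sample-size figure is involved. The check compares the two rules and then sets them against the stopping rule and the testing schedule.

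**Step 1: the two rules.** Let A be ALT or AST at or above 1.5 x ULN, and B be total bilirubin at or above 1.5 x ULN. Section 4.1.2 excludes on *A and B*. Appendix 4 excludes on *A or B*.

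| Screening result | Section 4.1.2 | Appendix 4 |
|---|---|---|
| Neither | not excluded | not excluded |
| A only | not excluded | excluded |
| B only | not excluded | excluded |
| Both | excluded | excluded |

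Section 4.1.2 excludes 1 combination of 4 and Appendix 4 excludes 3. They disagree on 3 - 1 = 2, the two single-abnormality cases.

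**Step 2: against the stopping rule.** The A-only case has no upper bound in the Section 4.1.2 bullet. It splits at the Appendix 5 limit:

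- ALT or AST at or above 3 x ULN with bilirubin below 1.5 x ULN: not excluded by the bullet, yet already at the level that requires discontinuation.
- ALT or AST from 1.5 to below 3 x ULN with bilirubin below 1.5 x ULN: not excluded by the bullet, and also below the numeric stopping limit.

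Under the Appendix 4 rule neither can enter. The entry limit of 1.5 x ULN lies below 3 x ULN, so nobody eligible on screening values would already meet the ALT/AST stopping rule.

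**Step 3: scheduled liver tests around dosing.** Group 1 is tested on Day 1 and Day 28, an interval of 28 - 1 = 27 days. Group 2 is tested on Day 44 and Day 72, an interval of 72 - 44 = 28 days. No liver test is scheduled between those visits, so a volunteer who enters with a raised value has no planned check until the end of the course.

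**Step 4: does the wording correct itself?** The BMI bullet in the same list joins BMI above 30 and BMI below 18 with *and*. Nobody can meet both, so every reader takes it as *or*. The liver bullet is different, because raised transaminases together with raised bilirubin is a recognisable clinical pattern. Section 8.3 and Appendix 5 use that conjunction, at higher limits, for reporting serious adverse events. A screener could reasonably take the *and* in Section 4.1.2 as intended.

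**The case against.** The best case against giving this much weight is that the intent is clear. Appendix 4 states the *or* rule with identical thresholds, Section 3.4 points to it, and the BMI bullet shows that the drafters used *and* loosely. The liver bullet can even be read as a list of two excluded groups.

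There are also more safeguards than the general health criterion. Volunteers must be clinically well and free of underlying conditions. Viral hepatitis, alcohol above 10 units a week, a positive drug screen and most concomitant drugs are excluded. Section 4.3 lets the investigator withdraw a subject. Section 7.5 contemplates stopping for clinically important liver-test rises without tying this to 3 x ULN. Group 2 has liver tests at screening and on Days 1, 28 and 44 by the time of its first dose. Starting dolutegravir on a known ALT of 3 x ULN would also contradict Appendix 5.

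Much of this stands as a limit on the practical effect. Passing one bullet is not the same as being eligible, and enrolment at 3 x ULN or above is unlikely with an attentive investigator. For isolated raised bilirubin, Appendix 5 has no stopping rule, so the safety argument rests mainly on ALT/AST.

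The objection does not remove the inconsistency. The added safeguards are discretionary or indirect, and none sets a numeric limit on liver tests at entry. Section 4.1.1 does give numeric ranges for blood counts, so leaving liver tests to judgement would be out of keeping with the rest of the criteria.

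**Conclusion.** The concern holds. The two current texts contradict each other in two of four combinations, and the weaker one is in the operative eligibility list. This should be fixed for participant safety and for consistent eligibility decisions. It has no bearing on sample size, power or the equivalence analysis.

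The conclusion rests on a literal reading of the Section 4.1.2 bullet. How often volunteers present with a single abnormality is not given and cannot be derived, so the count of two combinations describes the logical disagreement and not a frequency.

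**What to change.** In Section 4.1.2 replace *and* with *or*, so that the bullet excludes ALT or AST at or above 1.5 x ULN, or total bilirubin at or above 1.5 x ULN. This matches Appendix 4 and needs no new clinical decision. The BMI bullet can be corrected in the same amendment.

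If the sponsor did mean to admit isolated elevations, Appendix 4 is the text to change, and the benefit-risk assessment should then say so. One of the two has to be amended in either case.

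The cost is a one-word protocol amendment and possibly a few more screen failures.
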